### Sample size and statistical power

#### Main trial

We estimate a total sample size of 1080 children with SAM (360 per arm) and 1080 children with MAM (360 per arm) will provide sufficient statistical power to demonstrate non-inferiority for each comparison, with a non-inferiority margin of relative 12.5%, assuming a recovery rate in the control of 76% and a loss to follow up of 15% (Table 4). The sample size will be smaller for analyses of relapse, because only recovered children will be included in the analysis. All calculations assume a one-sided  $\alpha = 0.05$  for non-inferiority and two-sided  $\alpha = 0.05$  for superiority analyses,  $\beta = 0.8$ , and 15% attrition. While the key objectives of this research are to evaluate effects of the alternative RUTFs on recovery and relapse, we consider as primary outcomes any outcome for which we have adequate power for clinically or policy meaningful effect sizes (5).

 Stata commands `ssi` for continuous outcomes and `artbin` for binary outcomes were used for non-inferiority analyses, and `power twomeans` for continuous outcomes and `power twoproportions` for binary outcomes were used for superiority analyses. Outcome proportions, means, or standard deviations were taken from relevant studies in literature as delineated in Table 4.

Table 4. Calculations of detectable effect sizes for all outcomes

Outcome	Outcome prevalence in the literature	Type of analysis	Non-inferiority margin (relative) with $\geq 80\%$ power (Non-inferiority)	Detectable effect size at 80% power (Superiority)	Rank of outcome
Anthropometric recovery at discharge	MAM recovery (with RUSF*): 73% (6); 73% (7); 85% (8)  SAM recovery: 55.4% (9); 82.3% (10); 76% (11); 71% (pooled estimate from meta-analysis) (12)	Non-inferiority	12.5% relative margin		Primary
Relapse to wasting within 3-months post-discharge	Post-MAM relapse: 30% within 3 months (13); 33% within 12-months (14)  Post-SAM relapse: 6.8% 3-month cumulative incidence (15); 24% 2-month cumulative incidence (16); 30% within 3-months (unpublished)	Superiority		Risk difference of 11%; Relative risk = 0.72	Primary
Length of stay (LOS) among recovered children	MAM: 36.4 days (SD 50.4 days)(17); 5.9 weeks (95% CI: 4.9, 7.0)(18) SAM: 56 days (assumed 41 day SD) (9)	Non-inferiority	MAM: 4.9 days; 12.5% relative margin SAM: 8 days; 12.5% relative margin		Primary

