Weight gain during treatment	MAM: 4.1 g/kg/day (SD = 3.0) (17), SAM: 3 g/kg/day (SD = 4.7) in 6-23 mo and 8.6 g/kg/day (SD = 4.7) in 24-59 mo (19)	Non-inferiority	MAM: 0.14 kg; 12.5% relative margin SAM: 0.91 g/kg/day; 12.5% relative margin		Primary
Anthropometry at discharge from treatment	MAM: All estimates from Fabiansen et al (20) WLZ: -1.52	Non-inferiority	MAM:		Primary

	
MUAC: 130.1 mm HAZ: -1.86 WAZ: -2.6 (assumed from SAM because estimates not available) Weight: 7.8 kg Height: 72.9 cm
 
SAM: All estimates from Kangas et al(9) WLZ: -1.9 MUAC: 125.9 mm HAZ: -2.3 WAZ: -2.6 Weight: 7.3 kg Height: 71.6 cm
		
WLZ: 0.2 z-scores; 12.5% relative margin MUAC: 6.8 mm; 5% relative margin HAZ: 0.2 z-scores; 12.5% relative margin WAZ: 0.4 z-scores; 12.5% relative margin Weight: 0.4 kg; 5% relative margin Height: 3.8 cm; 5% relative margin
 
SAM: WLZ: 0.3 z-scores; 12.5% relative margin MUAC: 6.3 mm; 5% relative margin HAZ: 0.3 z-scores; 12.5% relative margin WAZ: 0.4 z-scores; 12.5% relative margin Weight: 0.4 kg; 5% relative margin Height: 3.8 cm; 5% relative margin
		
Anthropometry at 3-months post-discharge	MAM: All estimates from Fabiansen et al (20)	Superiority		MAM: WLZ: 0.26	Primary

	WLZ: -1.52 MUAC: 130.1 cm HAZ: -1.86 WAZ: -2.6 (assumed from SAM because estimates not available) Weight: 7.8 kg Height: 72.9 cm  SAM: All estimates from Kangas et al(9) WLZ: -1.9 MUAC: 125.9 cm HAZ: -2.3 WAZ: -2.6 Weight: 7.3 kg Height: 71.6 cm			MUAC: 2.46 cm HAZ: 0.39 WAZ: 0.37 Weight: 0.39 kg Height: 1.87 cm  SAM: WLZ: 0.37 MUAC: 3.13 cm HAZ: 0.48 WAZ: 0.37 Weight: 0.55 kg Height: 2.76 cm	
Hemoglobin at discharge	MAM: 108 g/L (SD = 13) (21) SAM: 108.6 g/L (SD = 11.2) (22)	Non-inferiority	MAM: 2.7 g/L; 2.5% relative margin SAM: 2.2 g/L; 2.5% relative margin		Primary
Hemoglobin at 3-months post-discharge	MAM: 108.0 g/L (SD = 13) (21) SAM: 108.6 g/L (SD = 11.2) (22)	Superiority	--	MAM = 2.9 g/L SAM = 2.9 g/L	Primary
Default from treatment	MAM: 6.8% (17) SAM: 8.5% (9)	Non-inferiority	MAM: 50% relative margin SAM: 45% relative margin		Secondary
Transfer to inpatient treatment	MAM: 5.8% (20) SAM: 20.1% (9)	Non-inferiority	MAM: 70% relative margin SAM: 40% relative margin		Secondary
Non-response to treatment	MAM: 32.2% (18), 28%(20) SAM: 12.5% (9)	Non-inferiority	MAM: 30% relative margin SAM: 25% relative margin		Secondary

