Compliance to treatment services (attendance at visits)	MAM: 87% (17) SAM: 11.1% (11)	Non-inferiority	MAM: 50% relative margin SAM: 10% relative margin		Secondary
Relapse to SAM	Note: Reporting of relapse as MAM vs SAM is not common. Daures et al reported 88.6% of relapses were MAM (23), so we apply this proportion to the below rates.  Post-MAM relapse to SAM: 30% within 3 months (13); 33% within 12-months (14)  Post-SAM relapse to SAM: 6.8% 3-month cumulative incidence (15); 24% 2-month cumulative incidence (16); 30% within 3-months (unpublished)	Superiority		MAM and SAM (Assumed to be same): RR = 0.34	Secondary
Relapse to MAM	Note: Reporting of relapse as MAM vs SAM is not common. Daures et al reported 88.6% of relapses were MAM (23), so we apply this proportion to the below rates.  Post-MAM relapse to SAM: 30% within 3 months (13); 33% within 12-months (14)  Post-SAM relapse to SAM: 6.8% 3-month cumulative incidence (15); 24% 2-month cumulative incidence (16); 30% within 3-months (unpublished)	Superiority	-	MAM and SAM (Assumed to be same): RR = 0.689	Secondary
Morbidity	MAM: 61.1% (any illness) (17) SAM: 60.0% (any illness) (9)	Non-inferiority	MAM: 17.5% relative margin SAM: 17.5% relative margin		Secondary

Anemia at discharge	MAM: 49% prevalence (21) SAM: 51% prevalence (22)	Non-inferiority	MAM: 17.5% relative margin SAM: 17.5% relative margin	--	Secondary
Anemia at 3-months post-discharge	MAM: 49% prevalence (21) SAM: 51% prevalence (22) *estimates are sourced from studies presenting data at discharge because post-discharge data not available	Superiority	--	MAM: 23.3% relative SAM: 24.2% relative	Secondary
Mortality		Non-inferiority			Exploratory

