## Statistical methods

We will conduct two separate comparisons between (i) the control group and SMS-RUTF, and (ii) between the control group and S-RUTF. All analyses will be done separately by wasting severity status (MAM vs SAM); that is, all analyses will be conducted and presented among MAM children and among SAM children separately. No adjustments for multiple comparisons will be made.

For binary outcomes, we will use log-binomial regression to estimate relative risks (RRs) and 95% confidence intervals (CIs) for the RRs, adjusting for any baseline factors as appropriate (described further below). If the regression model is adjusted, we will present both crude (unadjusted) and adjusted model results. If the models do not converge, we will use Poisson regression models with robust estimation of standard errors (26) and report which model was used. Non-inferiority will be declared if the lower bound of a one-sided 95% CI for the RR lies entirely below the non-inferiority margin of a relative 12.5%. For superiority analyses, we will use a two-sided 95% CI and superiority will be declared if the lower bound of the 95% CI for the relative risk is above 1.0. All analyses will be adjusted for health center to reflect the stratified randomization (27–29).

For continuous outcomes measured at one timepoint, we will use linear regression to estimate differences in that outcome between treatment arms, adjusting for any baseline factors as appropriate and health center (as explained above). Both unadjusted and adjusted model results will be presented.

For any outcome for which non-inferiority is demonstrated, we will then sequentially test for superiority. In these cases, we will report both non-inferiority and superiority results. The superiority analysis will be considered exploratory, as the study power calculations were based on non-inferiority effect size.

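### SAP Table 4 credits its non-inferiority margins with at least 80% power, but several secondary binary rows fall short, most clearly default, SAM non-response and SAM compliance

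*SAP*

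**What the plan says.** The SAP, under Sample size and statistical power, plans "1080 children with SAM (360 per arm) and 1080 children with MAM (360 per arm"), with 15% attrition and a one-sided alpha of 0.05 for non-inferiority. Protocol Table 4 gives the resulting analysed number as 306 per arm in each stratum. A footnote in the SAP names the Stata command artbin for binary non-inferiority outcomes, without its options.

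The relevant column of SAP Table 4 is headed "Non-inferiority margin (relative) with $\geq 80\%$ power (Non-inferiority"). Its secondary binary rows include:

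- Default (control rates 6.8% MAM, 8.5% SAM): "MAM: 50% relative margin SAM: 45% relative margin"
- Transfer to inpatient treatment (5.8% MAM, 20.1% SAM): "MAM: 70% relative margin SAM: 40% relative margin"
- Non-response (32.2% or 28% MAM, 12.5% SAM): "MAM: 30% relative margin SAM: 25% relative margin"
- Anemia at discharge (49% MAM, 51% SAM): "MAM: 17.5% relative margin SAM: 17.5% relative margin"; morbidity (61.1% MAM, 60.0% SAM) carries the same margins
- Compliance, meaning attendance at visits (87% MAM, 11.1% SAM): margins of 50% for MAM and 10% for SAM

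Statistical methods says that "all analyses will be conducted and presented among MAM children and among SAM children separately". It plans risk ratios for binary outcomes and names one margin for declaring non-inferiority, a relative 12.5%.

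**The concern.** A relative margin on an uncommon outcome is small in absolute terms. Half of 6.8% is 3.4 percentage points, and a quarter of 12.5% is 3.1 points. With about 300 children per arm, differences of that size cannot usually be excluded with 80% probability, so the column heading looked doubtful for these rows.

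Default, transfer and non-response are outcomes in which a poorer product could show itself. A reader who trusts the column will take a failed non-inferiority test as a result from an adequately powered comparison. If the true power is 30% to 50%, failure is the likely result even for a product identical to the control, and it says little.

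**Working it through.** **Inputs.** Control rate p and relative margin r come from SAP Table 4. One-sided alpha is 0.05 (z = 1.645). The analysed number n per arm and stratum is 306 (360 less 15%) or, most generously, 360. True rates are assumed equal in both arms.

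**Formulas.**
- Risk difference: power = Φ( r·p / √(2p(1−p)/n) − 1.645 )
- Risk ratio, adverse outcome, limit 1+r: power = Φ( ln(1+r) / √(2(1−p)/(n·p)) − 1.645 )

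**Check against the plan's own figures.** With a 10-point margin, the risk-difference formula gives 90.2% at 77% recovery and n = 306 (Protocol Table 4: 90.0%). At n = 360 it gives 85.4% at 55.4% recovery (85.6%) and 96.9% at 82.3% recovery (96.8%). The agreement is close, although it needs two different values of n. For recovery in the SAP (76%, margin 12.5%, n = 306) it gives 86.6%, consistent with at least 80%.

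**Worked example, default in MAM, n = 306.**
- Risk difference: margin 0.50 × 6.8% = 3.40 points; standard error √(2 × 0.068 × 0.932 / 306) = 2.035 points; 3.40/2.035 = 1.671; Φ(1.671 − 1.645) = 51%.
- Risk ratio: ln 1.5 = 0.405; standard error √(2 × 0.932 / (306 × 0.068)) = 0.299; Φ(1.355 − 1.645) = 39%.

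**Worked example, non-response in SAM, n = 306.**
- Risk difference: margin 3.125 points, standard error 2.674 points; Φ(1.169 − 1.645) = 32%.
- Risk ratio: ln 1.25 = 0.223, standard error 0.214; Φ(1.043 − 1.645) = 27%.

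**All rows (power, %).**

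| Row | p, r | Risk difference, n = 306 | Risk difference, n = 360 | Risk ratio, n = 306 |
|---|---|---|---|---|
| Default MAM | 6.8%, 50% | 51 | 57 | 39 |
| Default SAM | 8.5%, 45% | 52 | 58 | 40 |
| Non-response SAM | 12.5%, 25% | 32 | 35 | 27 |
| Compliance SAM, as printed | 11.1%, 10% | 11 | 12 | 11 |
| Transfer MAM | 5.8%, 70% | 69 | 75 | 49 |
| Anemia MAM | 49%, 17.5% | 68 | 74 | 62 |
| Anemia SAM | 51%, 17.5% | 71 | 77 | 65 |
| Non-response MAM | 28%, 30% | 75 | 81 | 65 |
| Non-response MAM | 32.2%, 30% | 82 | 87 | 72 |
| Transfer SAM | 20.1%, 40% | 80 | 85 | 67 |
| Morbidity MAM | 61.1%, 17.5% | 86 | 90 | 80 |
| Morbidity SAM | 60.0%, 17.5% | 84 | 89 | 79 |

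Compliance is a favourable outcome, so its risk-ratio limit would be 1−r. That gives 12% instead of 11%. Simulation agreed with the adverse-outcome rows to within about one point.

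**Number needed.** For 80% power on the risk-difference scale, the analysed n per arm would be 678 (default MAM), 658 (default SAM), 1385 (non-response SAM), 410 (transfer MAM), 421 (anemia MAM) and 388 (anemia SAM). Each stratum enrols 360 per arm.

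**Compliance margins.** Exchanging the two printed margins gives risk-difference power at n = 306 of 94% for MAM (87%, 10%) and 71% for SAM (11.1%, 50%). As printed, the MAM margin is 43.5 points and the SAM margin 1.1 points. The pattern suggests a swap but does not prove one.

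**The case against.** The strongest reply is that the exact calculation is unknown. The SAP does not give the artbin options or the anticipated rates in the intervention arms. Rows that agree with the column show only that the formula is compatible with it. Two of them are fragile: SAM transfer is 79.9% at 306 per arm, and MAM non-response passes at 306 only with the 32.2% rate. This stands, and the point does not depend on knowing the method used. Among the alternatives tried, log risk ratio against 1−r at 360 per arm lifts default in MAM to 81% and anemia in MAM to 81%, but that is the wrong direction for an adverse outcome. It still leaves default in SAM at 79% and SAM non-response at 43%.

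A reader might infer that the default rows were computed with MAM and SAM pooled, because 720 per arm gives 82% and 83%. The documents do not say so, and SAM non-response reaches only 56% at 720. The explanation is conjecture.

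The SAP's missing-data section treats default as an outcome, so 360 per arm may be the fairer number for that row. It still gives only 57% and 58% on the risk-difference scale (43% and 45% on the risk-ratio scale).

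The SAP reserves primary rank for outcomes with adequate power, so secondary rank already hints at less. That limits the consequence, but the column heading still makes the 80% claim for these rows.

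Finally, Statistical methods names only a 12.5% margin, so the row margins may not be the ones tested. This stands as a matter to reconcile. It does not rescue the claim: a limit of 1.125 at 306 per arm gives only 10% to 14% for default, MAM transfer and SAM non-response.

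**Conclusion.** The claim of at least 80% power is wrong for several secondary rows. The shortfall is large for default in both strata, non-response in SAM and compliance in SAM as printed. It is smaller for MAM transfer and for anemia in both strata. MAM non-response depends on which listed rate is used. On the planned risk-ratio scale at 306 per arm, SAM transfer, MAM non-response at either rate and, by about one point, SAM morbidity also fall below 80%. For SAM non-response, a product identical to control would fail to be declared non-inferior about 68% of the time on the risk-difference scale and 73% on the risk-ratio scale.

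These figures assume equal true rates, the printed control rates, the Table 4 row margins and separate strata. It would be too strong to infer that the trial's main non-inferiority question is underpowered: the recovery calculation holds at the 76% rate and 12.5% margin that the SAP assumes.

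**What to change.** In SAP Table 4:

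1. Recalculate every binary non-inferiority row, not only the worst ones, on one stated scale that matches the risk-ratio analysis, in the direction appropriate to each outcome and at the per-stratum analysed number. Correcting some rows on the risk-ratio scale and leaving others on the risk difference would keep false entries in the column.
2. Check the compliance row for exchanged MAM and SAM margins.
3. Replace the 80% claim with the recomputed power wherever it is not met.
4. Reconcile the row margins with the single relative 12.5% in Statistical methods, so that each outcome has one margin for its test.
5. State that failure to show non-inferiority on the underpowered rows is inconclusive.

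The cost is one recalculation and some rewording. No extra children or data are needed. The price is that the stated power becomes less favourable.

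### The SAP gives two sets of non-inferiority margins without saying which decides; several Table 4 margins lack the stated 80% power, and the compliance row and discharge MUAC margins need correcting

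*SAP*

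**What the plan says.** SAP, Statistical methods: for binary outcomes, non-inferiority is declared if the "lower bound of a one-sided 95% CI for the RR lies entirely below the non-inferiority margin of a relative 12.5" (per cent). The sentence is not limited to recovery and does not point to Table 4.

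SAP Table 4 has a column headed "Non-inferiority margin (relative) with $\geq 80\%$ power (Non-inferiority". Its relative margins for secondary binary outcomes (MAM/SAM) are: default 50/45%, transfer 70/40%, non-response 30/25%, compliance 50/10%, morbidity 17.5/17.5% and anaemia at discharge 17.5/17.5%. None equals 12.5%.

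The compliance row, defined there as attendance at visits, gives control rates of "MAM: 87% (17) SAM: 11.1% (11") and margins of "MAM: 50% relative margin SAM: 10% relative margin".

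For MUAC at discharge, which the SAP ranks as primary, Table 4 gives expected means of 130.1 mm (MAM) and 125.9 mm (SAM). The margins are "MUAC: 6.8 mm; 5% relative margin" for MAM and "MUAC: 6.3 mm; 5% relative margin" for SAM. SAP Table 1 requires MUAC of at least 125 mm for recovery. Statistical methods gives no non-inferiority rule for continuous outcomes, so Table 4 is the only source of a MUAC margin.

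**The concern.** A non-inferiority margin has to be fixed before the data are seen. Here a reader can defend either 12.5% or the Table 4 figure, and the same data can pass one and fail the other. Table 4 also attaches a power claim to each margin, so a wrong claim misleads readers about what a failure to show non-inferiority means. Two sets of entries look wrong in themselves. The compliance row puts a very wide margin on a high rate and a margin of about one percentage point on a low one. The MUAC margins reach below the threshold that the trial uses to call a child recovered.

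**Working it through.** **Inputs.** 306 analysed per arm and stratum (protocol Table 4: 360 less 15%). One-sided alpha of 0.05 (SAP, Sample size and statistical power: "All calculations assume a one-sided $\alpha = 0.05$ for non-inferiority"). Control rates p and relative margins r from SAP Table 4. True rates are taken as equal in both arms.

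**Formulas.** Risk-difference power = Phi( p·r / sqrt(2p(1−p)/306) − 1.645 ). Log-RR power = Phi( |ln(1±r)| / sqrt(2(1−p)/(306p)) − 1.645 ), with 1+r for adverse outcomes and 1−r for compliance.

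**Check against the plan's own figure.** Protocol recovery, 77% with a 10-point margin: 0.10/sqrt(2×0.77×0.23/306) = 2.939, and Phi(2.939 − 1.645) = 90.2%, against 90.0% stated. The SAP recovery row (76%, relative 12.5%) gives 86.6%, so its claim of at least 80% is met.

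**Secondary rows.** Worked example, MAM default: 0.068×0.50 = 0.034; SE = sqrt(2×0.068×0.932/306) = 0.02035; Phi(1.671 − 1.645) = 51%.

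| Row | p | Table 4 margin | Power, risk difference | Power, log-RR | Risk-difference power if 12.5% governs |
|---|---|---|---|---|---|
| Default MAM | 6.8% | 50% | 51% | 39% | 11% |
| Default SAM | 8.5% | 45% | 52% | 40% | 12% |
| Transfer MAM | 5.8% | 70% | 69% | 49% | 10% |
| Transfer SAM | 20.1% | 40% | 80% | 67% | 19% |
| Non-response MAM | 32.2% | 30% | 82% | 72% | 28% |
| Non-response SAM | 12.5% | 25% | 32% | 27% | 14% |
| Compliance MAM | 87% | 50% | 100% | 100% | 99% |
| Compliance SAM | 11.1% | 10% | 11% | 12% | 14% |
| Morbidity MAM | 61.1% | 17.5% | 86% | 80% | 62% |
| Morbidity SAM | 60.0% | 17.5% | 84% | 79% | 60% |
| Anaemia MAM | 49% | 17.5% | 68% | 62% | 45% |
| Anaemia SAM | 51% | 17.5% | 71% | 65% | 47% |

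At Table 4's other MAM non-response rate (28%), risk-difference power is 75% with the 30% margin and 25% with 12.5%. For every adverse outcome the log-RR figure is the lower one, and RR is the planned effect measure. Using all 360 per arm does not rescue the short rows: default 57/58%, MAM transfer 75%, SAM non-response 35%, anaemia 74/77%, SAM compliance 12%.

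**Does the choice of margin matter?** For adverse outcomes I use the upper bound, although the SAP sentence says lower, because only the upper bound can exclude an excess. With equal observed rates the bound is exp(1.645·sqrt(2(1−p)/(306p))).
- SAM transfer: exp(1.645×0.1612) = 1.30, fails 1.125, passes 1.40.
- MAM anaemia: exp(1.645×0.0825) = 1.145, fails 1.125, passes 1.175.
- MAM default: exp(1.645×0.2993) = 1.64, fails both 1.125 and 1.50.

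**Compliance row.** MAM: 87% × (1 − 0.50) = 43.5% is the boundary. SAM: 11.1% × 0.10 = 1.1 percentage points, which would need 9,904 per arm for 80% power. Exchanging the margins gives 94% (MAM) and 71% (SAM). Reading 11.1% as non-attendance gives 88.9% attendance, and a 10% margin then has 97% power.

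**MUAC at discharge.** Boundaries: 130.1 − 6.8 = 123.3 mm and 125.9 − 6.3 = 119.6 mm. Five per cent of 125.9 is 6.3, as printed, but 5% of 130.1 is 6.5, not 6.8. No discharge SD is printed. As an assumption, I back-calculate one from the 3-month detectable differences (2.46 and 3.13, printed as cm, read as mm), using SD = difference / (2.80·sqrt(2/n)) with n from 236 to 306: 9.5 to 10.9 mm (MAM) and 12.1 to 13.8 mm (SAM). The margin with 80% power at 306 per arm is 2.486·SD·sqrt(2/306): 1.9 to 2.2 mm (MAM) and 2.4 to 2.8 mm (SAM). With the printed 6.3 mm margin, a SAM arm with a true mean of 122.9 mm would be declared non-inferior in about 90% to 96% of trials.

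**The case against.** The best defence is that Table 4 is titled as a table of detectable effect sizes and serves to rank outcomes by power, so that 12.5% is the only decision margin. That reading is possible, and it removes the wide margins for binary outcomes. But no text states it, the column is labelled as a non-inferiority margin, and the secondary binary outcomes other than MAM compliance would then be tested with 10% to 62% power.

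Several stronger inferences should be resisted.
- A reader might infer that halved attendance would count as non-inferior. That requires Table 4 to govern, and even then a true 43.5% is the boundary and passes only about 5% of the time. A true 50% against 87% would pass in 60% (risk difference) to 74% (log-RR) of trials.
- A reader might infer that the compliance margins were swapped. The control rates could have been exchanged instead, or the rows could mix attendance with non-attendance: 13% non-attendance with a 50% margin has 77% power at 306 per arm. The cited sources would settle this, and the documents do not.
- A reader might infer that the MUAC margin passes an arm of unrecovered children. Each recovered child must have MUAC of at least 125 mm, recovery is tested separately, and this outcome is an arm mean over all children at end of treatment. For SAM the control mean is only 0.9 mm above the cut-off, so any margin over 0.9 mm crosses it. Crossing 125 mm cannot by itself be the test of a SAM margin.

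These points limit the claim. They do not explain the contradiction, the power shortfalls or the compliance row.

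**Conclusion.** The point holds. The SAP has two incompatible sets of margins for secondary binary non-inferiority outcomes and no rule for choosing between them. Recovery, at 12.5% in both places, is unaffected. The choice changes the result in some rows (SAM transfer, anaemia) and not in others (MAM default), so it would be wrong to say that every conclusion turns on it.

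The power claim fails for default in both strata, MAM transfer, SAM non-response, anaemia in both strata and SAM compliance. This rests on equal true rates, the table's own control rates and 306 per arm, using a method that reproduces the protocol's recovery power.

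The compliance row is wrong as printed, but its cause is not established. The MUAC margins are wide against the recovery cut-off, and the MAM figure does not match its 5% label. How much tighter they could be depends on an SD that the documents do not print, so the range of 1.9 to 2.8 mm is conditional and is not a recommended margin.

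**What to change.** In Statistical methods, limit 12.5% to recovery. For every other non-inferiority outcome, state one pre-specified decision margin and its direction: upper bound for adverse outcomes, lower bound for outcomes where higher is better. Make Table 4 agree, and say whether its column holds decision margins or detectable sizes.

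Check the compliance rates, their coding and their margins against the cited sources, and correct the row.

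Justify each margin on clinical or policy grounds. Do not widen margins until they reach 80% power: for MAM default that would take about 74%, and for MAM transfer about 81%. Print the true power of each row, and report underpowered outcomes descriptively.

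For MUAC at discharge, print the SD used, correct the 6.8 mm or its 5% label, and re-justify a tighter margin.

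All of this is SAP text and needs no new data. The price is that some secondary non-inferiority claims, and the MUAC claim, become harder to make or are shown to be underpowered.

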We estimate a total sample size of 1080 children with SAM (360 per arm) and 1080 children with MAM (360 per arm) will provide at least 90% statistical power to demonstrate non-inferiority for each comparison, with a non-inferiority margin of 10 percentage points, assuming a recovery rate in the control of 77% (Table 4). For relapse outcomes, sample size will be smaller, and thus power will be lower, because only recovered children will be included in the analysis. All calculations assume a one-sided $\alpha = 0.05$ for non-inferiority and two-sided $\alpha = 0.05$ for superiority analyses.

Table 4. Sample size calculations

Scenarios with at least 80% power are **bolded**.

Primary outcome	Analysis type	Sample size per arm	Outcome prevalences reported in literature	Non-inferiority margin or detectable effect size	Assumption on control group outcome prevalence/means in sample size calculations	Power per comparison
Anthropometric recovery at discharge	Non-inferiority	360 MAM and 360 SAM children/arm enrolled; 306 MAM and 306 SAM children in analysis after 15% attrition	MAM recovery (with RUSF*): 73% (13); 73% (14); 85% (15) SAM recovery : 55.4% (16); 82.3% (17); 76% (18); 71% (pooled estimate from meta-analysis) (19)	10 percentage points (absolute difference)	55.4% (vs 45.4%)	85.6%
					77.0% (vs 67.0%)	90.0%
					82.3% (vs 72.3%)	96.8%
Relapse to wasting within 3-months post-discharge	Superiority	236 children/arm in analysis (assuming 77% of the 306 children recover)	Post-MAM relapse : 30% within 3 months (period prevalence) (20); 33% within 12-months (21) Post-SAM relapse : 6.8% 3-month cumulative incidence (22); 24% 2-month cumulative incidence (23); 30% within 3-months (unpublished); 2.6 episodes per child-year (unpublished); 1.3	35% relative reduction (incidence rate ratio = 0.65)	Incidence of 2.6 episodes per child-year	80.0%
					Prevalence of 30% (vs 20%)	71.0%

			episodes per child-year (unpublished)			
--	--	--	--	--	--	--

*RUSF = ready-to-use supplementary food

Study procedures

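### SAP Table 4's detectable effect for relapse to SAM (RR 0.34 at 80% power) does not reproduce: the row's own inputs give about 37% power

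*SAP*

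**What the plan says.** SAP Table 4 (Sample size and statistical power, Main trial) has a column headed "Detectable effect size at 80% power (Superiority)". In the relapse-to-SAM row the entry is "MAM and SAM (Assumed to be same): RR = 0.34", so one value serves both severity strata. The row explains its base rate: one cohort "reported 88.6% of relapses were MAM (23), so we apply this proportion to the below rates". The rates that follow include "Post-MAM relapse to SAM: 30% within 3 months (13); 33% within 12-months (14)" and, after SAM, 6.8%, 24% and 30%.

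The text above the table gives 360 children per arm in each stratum, 15% attrition, 76% recovery in the control arm, and relapse analysed in recovered children only. The footnote names a Stata two-proportion power command for binary superiority outcomes. Under Statistical methods, MAM and SAM are analysed separately, and "For superiority analyses, we will use a two-sided 95% CI". Protocol Table 4 gives the relapse analysis set as "236 children/arm in analysis (assuming 77% of the 306 children recover)".

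Relapse to SAM is ranked secondary and is to be tested for superiority. The row prints no control risk and no n.

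**The concern.** If 11.4% of relapses are to SAM and relapse is at most about 30% in three months, relapse to SAM is rare: about 8 control-arm events in 232 children. A relative risk of 0.34 then means about 8 events against 3, which a trial of this size would usually fail to separate. Such counts do not fit a claim of 80% power.

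What is at stake is interpretation. A reader who trusts Table 4 would take a non-significant result as fair evidence against a two-thirds reduction in relapse to SAM. At 37% power, such a reduction would be missed about 63% of the time.

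**Working it through.** **Inputs**
- SAM share of relapses: 100% − 88.6% = 11.4% (SAP Table 4).
- Control risk: 0.114 × 30% = 3.42%. The other listed rates give 3.76% (33%, a 12-month figure), 2.74% (24%) and 0.78% (6.8%).
- n per arm: SAP 360 × 0.85 × 0.76 = 232.6, taken as 232. Protocol: 306 × 0.77 = 235.6, printed as 236.
- Two-sided alpha 0.05, 1:1 comparison, pooled-variance two-proportion test.

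**The plan's figure: RR 0.34 at 80% power**
- Intervention risk: 0.34 × 3.42% = 1.16%. Difference: 2.26 percentage points.
- Mean risk 2.29%. Null SE = √(2 × 0.0229 × 0.9771 / 232) = 0.01389.
- Alternative SE = √((0.0342 × 0.9658 + 0.0116 × 0.9884) / 232) = 0.01385.
- Power = Φ((0.02257 − 1.96 × 0.01389) / 0.01385) = Φ(−0.336) = 36.8%.
- At n = 236: 37.4%. Exact enumeration of the same test at n = 232: 36.4%.

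The 80% is not reproduced.

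**Can another input rescue it?**

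| Variation | Power for RR 0.34 |
|---|---|
| Control risk 3.76% (n = 232) | 40% |
| Control risk 2.74% (n = 232) | 30% |
| Control risk 0.78% (n = 232) | 12% |
| Everyone recovers (n = 306) | 46% |
| No attrition either (n = 360) | 53% |
| One-sided 0.05 (n = 232) | 49% |
| Fisher's exact test (n = 232) | 25% |

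At a 3.42% control risk, 80% power for RR 0.34 needs 689 analysed children per arm, about three times 232. At the planned n it needs a control risk of 9.7% (n = 232) or 9.5% (n = 236).

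**Where 0.34 may come from**

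Take 3.42% as the lower rate and solve for the higher rate detectable at 80% power. This gives 9.89% (n = 232) or 9.82% (n = 236), and ratios of 3.42/9.89 = 0.346 and 3.42/9.82 = 0.348, close to the printed 0.34.

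For relapse to MAM the base is 0.886 × 30% = 26.58%. The same step gives higher rates of 38.75% and 38.64%, and ratios of 0.686 and 0.688, against the printed 0.689. As a reduction from 26.58%, RR 0.689 has only 57% (n = 232) to 58% (n = 236) power.

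**What is detectable at 3.42%**

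The normal approximation gives RR 0.01 (n = 232) to 0.02 (n = 236), but it fails with about 8 events against 0.2 or fewer. Exact enumeration of the uncorrected chi-square test gives 92% power at RR 0.02 (n = 236). It reaches 80% at RR 0.074 (n = 232) or 0.077 (n = 236).

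**The case against.** **The control risk is not printed.** This is correct: 3.42% is derived, and the row labels its rates as relapse to SAM. But the same figures appear as total relapse in the relapse-to-wasting row, and the note says the split is applied to them. Taken literally as relapse to SAM, the rates of 24%, 30% and 33% lie well above the 9.7% that RR 0.34 requires, and 6.8% lies below it. RR 0.34 would still not be the 80% effect for any listed rate.

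**The SAP expects 10% relapse elsewhere.** A control risk near 10% would support RR 0.34. That figure belongs to the microbiome sub-study's sample size and means any relapse. Applying the 11.4% share to it would give 1.1%.

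**The outcome is secondary.** This stands. The SAP reserves primary rank for outcomes with adequate power for meaningful effects, so it already signals limited sensitivity here. The error changes no sample size, outcome rank or analysis method.

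**Stronger readings.** A reader might infer that the superiority test should be dropped, or that a null result says nothing. The documents support neither. Low power does not invalidate a prespecified two-sided 5% test. With 3.42% in both arms and n = 236, the 95% CI for the risk difference has half-width 1.96 × √(2 × 0.0342 × 0.9658 / 236) = 3.3 percentage points, which bounds large absolute harm. It is wider than the 2.26 points that RR 0.34 represents, so such a result could not exclude that reduction.

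**Conclusion.** Wrong as written. Under the inputs that the row implies, RR 0.34 for relapse to SAM has about 37% power, not 80%; the other listed rates give 12% to about 40%. This rests on applying the 11.4% share to the listed totals, on 232 to 236 recovered children per arm, on separate strata and on two-sided 0.05. None of the plan's listed rates brings the figure near 80% at the planned n.

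The inverted-ratio explanation is an inference, since the SAP shows no working; the 37% does not depend on it. That two rows nearly fit the same step is reason enough to recompute the relapse-to-MAM row. The consequence is limited to how a secondary result is read. The recovery analysis and the trial's sample size are unaffected.

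**What to change.** - In the relapse-to-SAM row, state the control risk, the n per arm and the method.
- Replace the entry with about 37% power for RR 0.34, or with a detectable RR from an exact calculation (about 0.07 to 0.08 for the uncorrected chi-square test at a 3.42% control risk). Do not print the normal-approximation value of 0.01 to 0.02. Name the test, because a continuity correction or Fisher's test would give a different value.
- Recompute the relapse-to-MAM row, with its control risk and n stated.
- Keep the superiority test as a secondary analysis. Add that a non-significant result will be reported with its confidence interval and not read as evidence against a large reduction.

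The cost is SAP wording and a short recalculation. The stated sensitivity becomes less favourable; design, conduct and sample size do not change.
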